1.0 Objectives / Specific Aims

Overview: Chronic pain and fatigue are among the most pervasive and expensive health complaints in the United States, with 53% of adults aged 65 and older (about 18.7 million) reporting pain at any one time (Patel et al., 2013), and 31% of those over 51 reporting fatigue.¹ **Adults, and older adults in particular with pain and fatigue, have reduced ability to successfully Age in Place, as these symptoms can impact activities of daily living, increase fall risk²⁻⁶ and diminish mental health and subsequent motivation to remain physically active.** Unfortunately, integrated programs to address pain and fatigue, and thereby increase likelihood of aging in place, such as those that target muscle tone, mobility, strength and mental health are not common, and those that exist may be beyond the reach financially and logistically to poor older adults who might most benefit from them.

This project proposes to evaluate feasibility of **Activate for Life**, an integrated home-telehealth delivered intervention that combines **Otago +Yoga + Behavioral Activation** to address both physical and mental health factors to increase likelihood of successful Aging in Place. The Otago Exercise Program (OEP) focuses on strength and balance training⁷, and is endorsed by the CDC⁸ as an effective fall prevention intervention^{8,9}; Yoga (including *asana*/poses and *pranayama*/breathing;) emphasizes balance and stretching, and can be practiced even by individuals with significant physical disabilities, and Behavioral Activation (BA) addresses withdrawal and social isolation to enhance mental health and is an evidence based intervention for depression validated with older adults, including validation of its effectiveness by our team, when delivered via home based telehealth¹⁰⁻¹².

PREMISE: This project conceptualizes factors that negatively influence aging in place, namely pain, fatigue and mental health problems within the socio-ecological model to explain the multiple dynamic and complex influences that impact their presentation. For example, pain and fatigue in older adults may reduce their mobility, which reduces muscle tone and increases risk of falls. Reduced mobility also contributes to social isolation, thereby increasing depression and further reducing motivation to engage in exercise. These factors constitute a negative feedback loop, amplified in many older adults by limited income and resources, that perpetuate deterioration in both physical and mental spheres, leading to reduced ability to Age in Place. Therefore, the potential benefit of a comprehensive, integrated treatment, delivered directly into older adults' homes via telehealth technology, to address both physical and emotional health dimensions, as well as limited access to transportation, is high.

Preliminary pilot data on telehealth-delivered Otago Exercise Program revealed high rates of participation and satisfaction, and most important, significant improvement in physical stability and movement. However, high levels of anxiety and depression were observed, indicating a potential need to complement Otago with mindfulness and action-based strategies to reduce negative mental health symptoms while addressing pain and fatigue symptoms. We subsequently added Yoga and telehealth delivered Behavioral Activation to the program in one series of participants and would like to fully explore the effectiveness of this integrated intervention.

Thus, the **Overall Aim** of the present proposal is to evaluate the feasibility of an integrated mind-body intervention, *Activate for Life*, to improve overall physical activity and mental health and reduce pain and fatigue, resulting in increased likelihood of Aging in Place. Both subjective self-report (i.e., NIH PROMIS measures of pain, fatigue, depression and anxiety) and objective accelerometer data will be collected, along with standardized measures of balance, strength, and stability. In addition, the measures will be complemented with biomarker-based measures of stress, including cortisol based and 1,5-AG assays before, during, and after treatment that are correlated with stress, and fatigue symptoms.

Thus, the Specific Aims of the project are to:

AIM 1. Integrate evidence-based components of “*Activate for Life*” a telehealth delivered, nurse-led behavioral health program for low income older adults targeting pain and fatigue through balance training (Otago), strengthening and mindfulness (Yoga), and affective state (Behavioral Activation).

We hypothesize that the evidence-based Otago and Yoga components of this intervention will integrate with the ‘infrastructure’ format of the Behavioral Activation mental health treatment insofar as a 60-minute session, 6-10 session intervention will be developed.

Aim 2. Test the feasibility of Activate for Life in terms of its individual components by comparing Otago vs. Otago+Yoga vs. Otago+Yoga+Behavioral Activation in a pilot RCT design with 10 participants in each of the 3 conditions in terms of recruitment, intervention ‘dosage’ (frequency/density), adherence, treatment satisfaction, attrition, rates of missing data, and other feasibility metrics, including qualitative feedback from participants for final intervention refinement.

We hypothesize that adherence will be adequate (65% scheduled activity compliance), satisfaction will be high (above 80%), attrition will be limited (below 25%), and followup data collected (below 20% missing data)

AIM 3. Determine an initial efficacy signal for the intervention that will inform future power estimates.

We hypothesize that the combined intervention will show significant within subject improvement over baseline on measures of pain, fatigue, and depression.

Supplemental ARM 4 - AIM 4. Test the feasibility of a 12-week e/mHealth gentle yoga+yogic breathing (GYYB) intervention for alleviating symptoms of burden in aging Caregivers (CG) of persons (N=20) with dementia (PWD); measure initial changes in stress and QoL indicators in CG and PWD (post- vs. pre-intervention).

Impact. This pilot feasibility study will set the stage for a full scale RCT demonstrating the additive benefit (if present) of each additional component over the CDC approved balance intervention Otago. Self-management of pain and fatigue through strength and balance training in low-income older adults can improve quality of life, decrease health care costs, and increase the ability of the person with these symptoms to age in place.

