Preliminary studies. Preliminary pilot data on telehealth-delivered Otago Exercise Program revealed high rates of participation and satisfaction, and most important, significant improvement in physical stability and movement. However, high levels of anxiety and depression were observed, indicating a potential need to complement Otago with mindfulness and action-based strategies to reduce negative mental health symptoms while addressing pain and fatigue symptoms. We subsequently added Yoga and telehealth delivered Behavioral Activation to the program in one series of participants and intend to fully explore the effectiveness of this integrated intervention.

INNOVATION: Otago only does balance and strengthening, y+O does balance and strengthening, and pain control, adding ba addresses motivation and depression so Activate for Life adds motivation

An interprofessional (IP) team of nursing, physical therapy and behavioral health clinical researchers will be collaborating to develop “Activate for Life” to address pain and fatigue by increasing physical activity and self- efficacy in low-income elderly. This project is innovative in the following ways:

- Integrates mHealth and eHealth

- Uses eHealth (televideo) to deliver interventions directly into participant's homes, dramatically enhancing convenience and overcoming barriers related to rurality
- Uses real time (EMA) activity monitoring and feedback with easily understood data presentation graphics to inform both patient and provider on progress through an application (app) on the tablet
- Uses ECA to assess parameter violations and trigger televideo visit for motivation/problem solving session with nurse

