10.0 Study Design / Methods

ARMS 1, 2, and 3: Once a participant has consented and been enrolled they will be randomized by computer (stratified by gender) to one of three treatment groups and the PI and/or their designee will set up a home visit appointment to meet with the participant to obtain baseline data (Table 1). Part of the baseline screening includes the PROMIS Emotional Distress-Depression Short Form 8a. If a participant scores in the severe depression category (raw score 33 and above) a referral will be placed to a mental health professional. Additionally, participants that score in the moderate depression category (raw score 23 to 32) further screening for suicidal ideation will take place. If the participant would admit to suicidal ideation at any time during the study, an emergent mental health consult will be placed through the Charleston/Dorchester Mental Health Center Assessment/Mobile Crisis.

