restatement of the rationale (ie., that what one does affects how one feels and doing positive things will help one to feel positively), and problem solving. Behaviors that were consistently planned but not completed are removed and alternative behaviors suggested. The next 2 days' activities are planned. This session usually involves a significant amount of problem solving, and identification of avoidance, with planning in place to counter this avoidance. Sessions 3-4: These sessions begin with a review of homework, followed by asking the patient to state, in their own words, their interpretation of the rationale for Behavioral Activation. Obstacles to completing behaviors are discussed and additional exposure-based and reinforcing behaviors are generated. The next 2 day's activities are planned. Session 5: Includes discussion of the rationale and treatment gains obtained thus far. Discussion is also centered on the need to continue planning activities and using a daily planner for at least 6 months. Relapse prevention strategies are reviewed. Additional sessions are conducted every other week until week 12 (Otago and GYYB completion).

Table 2: Measurements/Instruments/Interventions and Time Points		
Major tasks and domains; monitor/ evaluate	Measures/instruments/questions and Cronbach's alpha ()	Data sources and time points
Screening	Ability to ambulate 150 feet with or without assistive device; Short version of Test for Functional Health Literacy in Adults (0.97) ³⁷ Tablet Computer Familiarity Questionnaire (0.92) ³⁸ Mini-Cog ²⁶	Participant interview and observation; Baseline
Demographics	Personal health, medical, health history—co-morbidities, medications, use of pain medications, race/ethnicity	Participant interview; Baseline
Weekly nursing self-management	Review weekly diary entries, pain scores, yoga and /or Otago progress, fatigue, and sleep.	Weekly
Reach: Sample Recruitment	Progress monitoring of sample representativeness; types of recruitment activities and rates; % eligible, consented, oriented	Tracking forms; weekly quality checks by PI; weekly team meetings
Effectiveness: Functional impacts Pain	Numerical rating scale NRS (0.99) ³⁹ PROMIS Pain Interference Short Form 6b (0.98) ⁴⁰ PROMIS Pain Behavior Short Form 7a (0.98) ⁴⁰ PROMIS Fatigue Short Form 6a (0.91) ⁴¹	Baseline; Daily; Study end Baseline; Study end Baseline; Study end Baseline; Daily; Study end

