Official title: Activate For Life: mHealth Intervention To Address Pain And Fatigue In Lowincome Older Adults Aging In Place

NCT03853148

Document date: 03/12/2021

Analysis plan

Data were analyzed using IBM SPSS Version 26.0. Mean substitution was conducted to account for missing data (these did not represent more than 40% of overall dead data). Repeated measures analysis of variance (ANOVA) was used to determine significant differences for outcome variables between the 3 intervention Arms. Differences were considered statistically significant for *p*-values <0.05. Analyses were similar for outcomes in the caregiver group.

Measures of feasibility including recruitment and reach, fidelity and adherence, formal satisfaction, and drop-out proportions were evaluated. Then 95% confidence intervals for proportions were used to estimate dichotomous outcomes (e.g., the proportion of subjects who: agree to participate out of the number that are approached, the proportion who complete the intervention, the proportion who report satisfaction with the intervention, and the proportion who exit the study prematurely [drop out]). Further, the participants' reasons for drop out, and problems/issues encountered with the intervention were described via frequency distributions. For continuous measures (e.g. satisfaction scores), frequency distributions and the median and mean responses (with 95% confidence intervals) were obtained. Univariate descriptive statistics and frequency distributions were calculated as appropriate for all variables. Demographic variables obtained at baseline were described via measures of central tendency (mean, median), variability and frequency distributions as appropriate. Additionally, characteristics for those who were eligible for study versus those who were not eligible and for those who adhered to the study protocol (study completers) versus those who did not adhere (non-adherers and drop-outs) were compared to better describe the population for this study.

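### Aim 3's within-subject depression change in the combined arm mixes the programme with outside care that the protocol itself triggers, and Arms 1-3 do not record that care

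*Protocol*

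**What the plan says.** Aim 3 (Protocol 1.0) is to "Determine an initial efficacy signal for the intervention that will inform future power estimates". Its hypothesis is a before-after comparison inside one arm: "We hypothesize that the combined intervention will show significant within subject improvement over baseline on measures of pain, fatigue, and depression".

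Protocol 10.0 gives the depression form a second job. "Part of the baseline screening includes the PROMIS Emotional Distress-Depression Short Form 8a", and "If a participant scores in the severe depression category (raw score 33 and above) a referral will be placed to a mental health professional". Raw scores of 23 to 32 lead to further screening for suicidal ideation. There is also a route to outside care after baseline: "If the participant would admit to suicidal ideation at any time during the study, an emergent mental health consult will be placed". Section 15.0 repeats these rules for all participants. Table 2 lists the same 8a form as the depression outcome at baseline and study end.

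Severe depression is not an exclusion. Section 5.0 names psychiatric disability, but ties it to a Mini-Cog score of 0-2, which is a cognitive screen.

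Table 2 records "medications, use of pain medications, race/ethnicity" at baseline only. During the study the app logs pain medication, and the weekly review covers diary entries, pain, exercise progress, fatigue and sleep. The data analysis plan in Protocol 12.0 does not mention referral. Nor does the SAP, whose one named efficacy test is: "Repeated measures analysis of variance (ANOVA) was used to determine significant differences for outcome variables between the 3 intervention Arms".

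**The concern.** The participants with the most room to improve on the 8a are the ones the trial sends to outside care. If that care helps, their scores fall, and Aim 3 counts the fall as improvement under the combined intervention. A within-arm change has no comparison group to subtract this. Nor can it subtract regression to the mean: people picked out by a high first score tend to score lower the second time without any treatment.

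The number at stake is the one Aim 3 exists to produce. An effect size that includes referral care and regression would make a later trial of the programme too small. Because uptake and new treatment are not recorded, nobody could check afterwards how much of the change had another source.

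**Working it through.** **The plan's own figures.** Three arms of 10 give 3 × 10 = 30, as stated. The sample size rests on recruitment sites, so there is no power calculation to reproduce.

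**Inputs from the documents.** 10 participants in the combined arm (Protocol 1.0); referral at a baseline 8a raw score of 33 or above (10.0, 15.0); randomisation before the baseline visit (10.0); significance at 0.05 (SAP), taken here as two-sided.

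**Assumptions, since the documents give no figure.** The programme has no effect. Of the 10, k are referred, all take up care, and each falls by d raw points because of it. Change scores have standard deviation SD around those means. Ranges: k = 0 to 3, d = 5 to 12, SD = 4 to 8. Regression to the mean is not modelled and would add to the fall.

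**Within-arm change (Aim 3).** Spurious mean fall = k × d / 10. With d = 12 and k = 2 this is 2 × 12 / 10 = 2.4 points. A paired t-test on 10 people is significant when the observed mean change exceeds 2.262 / √10 = 0.72 SD. Simulated rates of a false significant improvement (100,000 to 200,000 runs per setting):

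| Referred, of 10 | Spurious mean fall, d = 5 to 12 | False-signal rate over all d and SD | d = 12, SD = 4 | d = 5, SD = 8 |
|---|---|---|---|---|
| 0 | 0 | 2.5% | 2.5% | 2.5% |
| 1 | 0.5 to 1.2 | about 4% | 3.8% | 3.5% |
| 2 | 1.0 to 2.4 | about 5-8% | 8.1% | 4.9% |
| 3 | 1.5 to 3.6 | about 7-19% | 18.8% | 6.8% |

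With d = 12 and SD = 4, the mean standardised change is 0.23, 0.39 and 0.54 for one, two and three referrals, although the programme does nothing.

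**Between-arm comparison (SAP).** With the same rule in every arm, 3, 6 or 9 of the 30 are referred at random across arms. A one-way ANOVA on change rejects in 4.8-5.1% of runs (SD 5, d = 8 or 10), so the nominal 5% holds. Chance imbalance remains in any single trial: the probability that two given arms differ by two or more referrals is 0.28, 0.41 or 0.47 for 3, 6 or 9 referred in all.

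**Dilution.** Let a share p of each arm receive outside care, let Behavioral Activation add δ in the others, and let it add δ' on top of outside care. The arm difference is (1 − p)δ + pδ'. If p = 0.2 and δ' = 0, it is 0.8δ. This is an illustration; the documents give neither p nor δ'.

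**The case against.** The strongest reply is that the SAP names no within-arm test. A reader might infer from the rates above that the trial's planned efficacy test is biased towards a false positive. The documents do not support that: the planned test compares arms, every arm has the same referral rule, and randomisation comes before the score that triggers it. The within-arm rates apply to the Aim 3 hypothesis only. But the SAP does not withdraw that hypothesis, so the reply limits the point without removing it.

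A second reply is that the size is guesswork. A reader might infer from the pilot, where "high levels of anxiety and depression were observed", that several referrals per arm are certain. The pilot statement gives no instrument, cut-off or proportion, and a referral placed is not care received within 12 weeks. With none or one referral in the arm the effect is minor. This stands, and it is itself a reason to record the count.

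A third reply is that before-after change in 10 people is weak evidence for other reasons too, such as natural course and attention. That is true. Recording referrals alone would not make the change interpretable, which is why the fix moves the signal to the arm difference.

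Finally, it is tempting to drop those who took up referral care and read the remaining change as the programme's own. Uptake follows randomisation and could differ by arm, since Behavioral Activation works on scheduling and barriers. Dropping these people also removes those most subject to regression to the mean. The before-and-after-exclusion difference would not isolate referral care.

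**Conclusion.** The point holds for Aim 3's within-subject depression result in the combined arm, and for any effect size taken from it. As planned, that change is programme plus any referral care plus regression to the mean, and no planned record would let anyone examine the referral part. Pain and fatigue would be touched only indirectly.

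The size is unknown. Under the stated assumptions of full uptake and no programme effect it is minor with one referral in ten and material with three. The between-arm ANOVA keeps its error rate; there the risks are dilution of Behavioral Activation's added effect and chance imbalance in referrals. The referral rule is a safety measure and is not in question. This is worth correcting because it changes what Aim 3 can conclude at little cost, but it does not undermine the feasibility aims.

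**What to change.** Leave the referral rule as it is, and make four changes.

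1. For Arms 1-3, record by arm at the week 12 and 3-month visits whether a mental health referral or consult was placed, whether it was taken up, and any new depression treatment.
2. Take the depression signal for future power from the between-arm difference in change, with its 95% confidence interval and all participants kept in.
3. Describe the combined arm's within-subject change as change under the programme plus any referral care.
4. As a sensitivity analysis only, show results with and without participants whose baseline 8a raw score was 33 or above. Baseline score defines this group, not uptake, so the comparison does not select on something that happened after randomisation.

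The SAP is written in the past tense. If the visits are over, changes 2 to 4 can still be made from scores the protocol already collects.

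The cost is a few questions at planned visits and one sensitivity analysis that will rest on very few people. The signal may look less favourable, and it will be less precise: with 10 per arm the 95% half-width for a two-arm difference is 2.101 × √(2/10) = 0.94 SD, against 0.72 SD for a single arm's change.

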2.0 Background

Aging in Place is by far, the preferred option for older adults from both the perspectives of older adults themselves, and the healthcare community. The population of older adults in the United States is growing rapidly and will double in size by 2060¹³. Older adults numbered 46.2 million in 2014, which represents about 14.5% of the total U.S. population¹³. By 2060 the projected number of older adults will be about 98 million¹³. However, this population is financially ill equipped to address care needs that often accompany aging, hence, maintaining health to ‘age in place’ is key. For example, in 2013 4.2 million (9.5%) older adults were below the poverty level¹³. This was an increase from 9.1% in 2012¹³. Another 5.6% or 2.5 million older adults were classified as “near poor” or having income between the poverty level and 25% above this level in the United States¹³. Not only is there a lack of resources to pay for qualified caregivers, and a lack of qualified caregivers themselves, there is also a lack of facilities to accommodate the elderly who may not be able to care for themselves in their home environment even if they could afford it¹⁴. This underscores the importance of interventions to facilitate aging in place, especially for the low-income elderly. Moreover, 90% of adults 65 and older prefer to age in place¹⁵. One of the main reasons for this is cost. The National Aging in Place Council reported that care per person annually can cost on average \$86,000 in a

nursing home, \$60,000 for someone in assisted living and \$23,000 for someone aging in place at home¹⁶. In addition, older adults view aging in place as being synonymous with increased quality of life. In fact, older adults fear losing independence (26%) and moving to a nursing home (13%) much more than they fear death (3%)¹⁷.

Pain and fatigue are significant barriers to aging in place. A retrospective study conducted in the United States based on the National Health and Aging Trends Study found the incidence of chronic pain in adults aged 65 and older to be 52.9% (about 18.7 million)¹⁸. Similarly, fatigue affects 31% of adults 51 years of age and older¹. Older adults with pain and fatigue are less likely to successfully age in place, as these symptoms can impact activities of daily living, reduce exercise, and increase fall risk^{2-6,19}. Programs to address pain and fatigue, such as those that target increasing mobility, are not always within the reach of these older adults, both literally, due to geographic isolation and rurality, and figuratively, due to cost. Indeed, low income older adults who suffer from pain and fatigue face a multitude of barriers that prevent them from participating in traditional physical activity or behavioral self-management programs. These include access to transportation, financial resources, ability to participate due to preexisting mobility problems, the need for assistive devices, being chair bound and or bed bound. Medicare does not cover programs to enhance aging in place through physical conditioning and self-management interventions, except in the small minority of instances where the Medicare eligible recipient is in need of Physical Therapy (PT) and determined to be: 1) homebound, 2) to qualify due to specific criteria, or 3) is under the order of their physician. In addition, PT for qualifying Medicare patients is episodic, or time and visit limited, and not ongoing²⁰. As such, PT, and PT under Medicare is not a viable option to address pain and fatigue in older adults.

The need for *Comprehensive* behavioral health pain and fatigue management programs.

Physical activity can improve strength and endurance, overall health, and quality of life among older adults with chronic conditions, which in turn may reduce hospitalizations and nursing home stays²¹. The impact of physical activity on joints may reduce a person's pain by improving flexibility, density and quality of connective tissues, and potentially on bony mass²². There is no evidence of increased pain with physical activities such as exercise, although this belief may be a barrier for older adults with pain in starting an exercise routine².

A large meta-analysis of self-management programs for pain reported by Taylor et al.²³ substantiated the need not only for a physical activity component for pain self-management programs, but also the addition of a supportive component that is delivered by health care providers. From this meta-analysis, Taylor et al.²³ also concluded that there was evidence that self-efficacy and depression at baseline can predict outcome and that pain catastrophizing and physical activity can mediate outcome from self-management²³, indicating that a mental health component may also be needed.

Three Evidence Based Programs that address aforementioned need and may, once integrated, enhance Aging In Place: Otago (Balance), Yoga (Strengthening and Mindfulness), and Behavioral Activation (Motivation and Affect).

Otago and Balance: Otago is a muscle strengthening and balance retraining program that can be delivered to the participant in their home. Otago was implemented and test in four randomized control trials of 1016 men and women aged 65-97 years of age. Findings from the trial showed that The Otago Exercise Program can reduce falls and fall related injuries, the program was most effective for adults 80 years and older, men and women benefited equally, and participants' strength and balance improved markedly as assessed by the Chair Stand and the Four-Stage Balance tests. The Otago exercise program is endorsed by the Centers for Disease Control as an effective fall intervention program for men and women¹⁹, decreasing falls in older adults by 35%.²⁰⁻²³

Gentle Yoga and Yogic Breathing (GYB) and Pain: In chronic pain, there is high contribution of the static load, due to habitual deep muscle tension that adversely affect microcirculation within muscles and the underlying viscera²⁴. Yoga reduces the electromyographic activity in the musculoskeletal system and promotes relaxation (Balambekar, 1969)²⁵. Awareness and progressive relaxation attained by Yoga practice could eliminate a substantial proportion of pain and the person feels more in control, which itself promotes pain reduction²⁴. Yoga influences the endocrine system by increasing local blood flow by gravity, muscle contraction and pressure release resulting in reduced abdominal pain²⁶. Muscle stretching could potentially lead to the release of endogenous opioids²⁷ thus could reduce the need for exogenous opioids. While pain modifies frequency, depth and pattern of respiration confining it to strained, shallow, and thoracic breathing, the practice of Pranayama with long exhalation cycles relaxes the musculoskeletal system, increases the tonicity of parasympathetic response, and reduces overall stress, which together could reduce pain²⁸⁻²⁹. Diaphragmatic breathing is probably the single most valuable thing that a patient in chronic pain can learn on the road to recuperation²⁴. Yoga practices, more commonly the ones involved in postures, has been used to test its usefulness in improving the quality of life in the aging population. In a pilot RCT in a community dwellers (mean age 68), the participants performed twice a week group yoga with an instructor for 12 weeks. The results showed the feasibility, and an improvement in balance and movement-related benefits³⁰. [name] (co-I) has developed a combination of gentle yoga and yogic breathing (GYB) program for people with limited mobility (GYB handout, [name]). The GYB program has been pilot tested among patients with scleroderma, and in a community dwelling elderly population and have shown feasibility, acceptance and a strong interest to continue the practice because of the perceived improvement (unpublished data).

Yoga and Biomarkers: The [name] lab (Co-I) has shown that acute practice of 20 minutes yogic breathing exercises stimulate salivary expression of nerve growth factor, immune response markers, and a reduction in inflammatory cytokines³¹⁻³³. In a recent study 90 minutes of Yoga practice among the elderly (mean age 60) has been shown to stimulate salivary immune function (increased salivary IgA and testosterone), and decreased stress hormones (cortisol)³⁴. Several recent studies have suggested saliva as a potential biomarker source in various physiological conditions^{35,36}. Due to the non-invasive collection method involved, and the availability of procedures to quantify stress, mood and pain related biomolecules saliva could be preferred over blood sampling among the elderly. Cortisol is a glucocorticoid hormone expressed in the saliva and is commonly used as an indicator of stress due to the activation of hypothalamus - pituitary - adrenal cortex (HPA) axis, and aging is associated with an increased levels of salivary cortisol (<https://www.ncbi.nlm.nih.gov/pubmed/27377692>). Yoga practice reduces the salivary cortisol level among older adults. 1,5-anhydroglucitol (1,5-AG) is a biomarker for hyperglycemia (<https://www.ncbi.nlm.nih.gov/pubmed/25249070>) and is found to be reduced in aging (<https://www.ncbi.nlm.nih.gov/pubmed/7835210>; <https://www.ncbi.nlm.nih.gov/pubmed/27036001>) . Both clinical and preclinical studies suggest that exercises could increase the levels of 1,5-AG (<https://www.ncbi.nlm.nih.gov/pubmed/15094482>; <https://www.ncbi.nlm.nih.gov/pubmed/28210043>). This will be the first study that fully examines the impact of yoga practice on the levels of 1,5-AG.

Behavioral activation (BA) and Depression. Behavioral Activation is a manualized treatment for depression (Lejuez, Hopko, & Hopko, 2001) that has gained support for its efficacy¹¹. Lejuez, Hopko, LePage, Hopko, & McNeil, 2001; Hopko et al., 2002). The primary goal of this intervention is to increase patients' engagement in social and healthy activities (e.g., interacting with supportive family and friends, community bingo, yoga, Otago) that are likely to produce reinforcement in the natural environment. Learning theory⁴⁷ forms the theoretical model supporting Behavioral Activation, which is hypothesized to reduce depression symptoms via increased frequency and density of reinforcing and personal values-consistent activities. This shift in balance of activities and reinforcement density

facilitates increased positive mood and cognitions (see^{47, 48}), and is achieved by first identifying, then operationally defining, and ultimately formally scheduling the aforementioned reinforcing or functionally useful behaviors. One of the strengths of BA, relative to other cognitive behavioral and activation-based interventions, is that it is designed to incorporate components of complementary treatments. Specifically, BA is heavily reliant on identifying and scheduling healthy behaviors, and on identify and resolving barriers to implementation of these scheduled behaviors. These healthy activities are often specifically derived from complementary interventions. As such, it may be conceptualized as an ‘framework’ intervention, upon which other intervention components, such as Otago and Yoga, can be hung.

Gap in knowledge related to using telehealth delivered programs to improve pain/fatigue and facilitate self-management in older adults. There is little literature regarding the use of mHealth (e.g., tablet based applications) and eHealth (e.g., televideo via tablet) as a platform for nurse-managed (and eventual self-managed) pain in older adults.²² A recent integrative review of the literature noted that a large proportion of older adults own a computer, tablet, and/or smartphone and regularly access the Internet.²² This review points out that while there is little evidence of using digital technology for pain management in older adults, using an interprofessional approach along with high quality interventions, strong technical support and training, and connectedness with clinicians and increased self-awareness through personal diaries may provide a strong platform for its use in clinical practice.²² Incidentally, none of the studies in this review addressed low-income older adults.

PREMISE: This project conceptualizes factors that negatively influence aging in place, namely problems associated with pain, fatigue and mental health, within the socio-ecological model to explain the multiple dynamic and complex influences that impact their presentation. For example, pain and fatigue in older adults may reduce their mobility, which reduces muscle tone and increases risk of falls. Reduced mobility also contributes to social isolation, thereby increasing depression and further reducing motivation to engage in exercise. These factors constitute a negative feedback loop, amplified in many older adults by limited income and resources, that perpetuate deterioration in both physical and mental spheres, leading to reduced ability to Age in Place. Therefore, the potential benefit of a comprehensive, integrated treatment, delivered directly into older adults’ homes via telehealth technology, to address both physical and emotional health dimensions, as well as limited access to transportation, is high.

Preliminary studies. Preliminary pilot data on telehealth-delivered Otago Exercise Program revealed high rates of participation and satisfaction, and most important, significant improvement in physical stability and movement. However, high levels of anxiety and depression were observed, indicating a potential need to complement Otago with mindfulness and action-based strategies to reduce negative mental health symptoms while addressing pain and fatigue symptoms. We subsequently added Yoga and telehealth delivered Behavioral Activation to the program in one series of participants and intend to fully explore the effectiveness of this integrated intervention.

INNOVATION: Otago only does balance and strengthening, y+O does balance and strengthening, and pain control, adding ba addresses motivation and depression so Activate for Life adds motivation

An interprofessional (IP) team of nursing, physical therapy and behavioral health clinical researchers will be collaborating to develop “Activate for Life” to address pain and fatigue by increasing physical activity and self- efficacy in low-income elderly. This project is innovative in the following ways:

- Integrates mHealth and eHealth

- Uses eHealth (televideo) to deliver interventions directly into participant's homes, dramatically enhancing convenience and overcoming barriers related to rurality
- Uses real time (EMA) activity monitoring and feedback with easily understood data presentation graphics to inform both patient and provider on progress through an application (app) on the tablet
- Uses ECA to assess parameter violations and trigger televideo visit for motivation/problem solving session with nurse

